## **1. Background, Review of the Literature, Significance**

Much of the morbidity and mortality with COVID-19 infection is thought to be the result of multisystem organ failure after a cytokine storm (Huang et al. *Lancet* 2020). This cytokine storm is very similar if not identical to the Secondary Hemophagocytic Lymphohistiocytosis (SHLH) seen in Severe Acute Respiratory Syndrom (SARS) also caused by a coronavirus, and includes increased levels of IL-2, IL-7, C-CSF, TNF-2, interferon-G inducible protein, MCP1 and MIP1a, all of which are driven by increased levels of IL-6. (Taraz 2013, Gobin, 2014) These findings have led to use of medications such as tocilizumab, an IL-6 receptor antagonist, to treat COVID-19 pneumonia. Fluoxetine and certain other selective serotonin reuptake inhibitors (SSRIs) have demonstrated in vitro and in vivo efficacy at reducing IL-6 and both preventing and treating hyperimmune responses associated with elevated levels of IL-6. Further, fluoxetine has a very safe therapeutic profile and could be used both prophylactically to prevent the cytokine storm with COVID-19, as well as an adjuvant treatment for critically ill patients.

[figure not shown]
*In vitro* and *in vivo* data demonstrate that fluoxetine and some other selective serotonin reuptake inhibitors (SSRIs) effectively reduce IL-6 to prevent hyperimmune response. In addition to SSRI use in adjuvant treatment for critically ill patients, the established safety profiles of many SSRIs allow these drugs to be used prophylactically in order to prevent cytokine storm associated with COVID-19 infections. SSRI treatment before starting antiviral therapies reduces incidence of interferon-induced depression and carries minimal side effect profiles consisting of rare dizziness (Udina et al., 2014). The SSRI fluoxetine demonstrates a particularly pronounced ability to inhibit IL-6 activation (Durairaj, Steury, & Parameswaran, 2015; Hashioka et al., 2007). This effect is mediated by non-serotonergic pathways involving NF-kB suppression and inhibition of dendritic cell antigen presentation (Branco-de-Almeida et al., 2011; D. Liu et al., 2011; R. P. Liu et al., 2014; Vollmar, Haghikia, Dermietzel, & Faustmann, 2008; Young et al., 2014). Animal models demonstrate that SSRIs protect against hyperinflammatory conditions and diseases states. In fact, pretreatment with fluoxetine frequently outperforms pretreatment with corticosteroids (Dong et al., 2016). Recently, clinical trials have demonstrated compelling relationships between SSRI treatment and cytokine levels (Amitai et al., 2016). A recent 2019 review and meta-analysis by Wang et al. echoes previous animal work and suggests that SSRI therapy indeed reduces IL-6 levels in human subjects (Wang et al., 2019).

These data are significant to COVID-19 patients at risk for pulmonary symptoms. Pretreatment with SSRIs results in decreased destructive immune reactions across a variety of animal models. In rat models of chronic obstructive pulmonary disease, fluoxetine decreases lung injury and inhibits cytokines such as TNF- $\alpha$  and IL-6 (Cai et al., 2017). Indeed, fluoxetine reduces inflammatory reaction in several models of human disease, providing marked decreases in reactive cytokines (Roumestan et al., 2007). In addition to decreasing expression of inflammatory cytokines, pretreatment with fluoxetine also decreases incidence of pulmonary arterial hypertension, pulmonary arterial muscularization, and extracellular matrix remodeling (Li et al., 2011). Bronchial asthma models show therapeutic effects of fluoxetine pretreatments in rats (Sherkawy, Abo-Youssef, Salama, & Ismaiel, 2018), and several studies suggest positive therapeutic efficacy may be concurrent with reduced levels of cytokines including IL-6 (Blatteau et al., 2012; Blatteau et al., 2015).

Overall, there is significant preclinical data supporting the use of SSRI's in the abrogation of harmful inflammatory side effects, such as those driving COVID19 morbidity and mortality. Furthermore, clinical data shows robust safety and efficacy profiles supporting the use of fluoxetine pretreatment interventions. At the University of Toledo Medical Campus, we are fortunate to have a leading expert on the relationship between antidepressant drugs and their anti-inflammatory therapeutic effects. [name], who will be leading the laboratory work described in this proposal, has published extensively on the use of antidepressants to limit organ damage, decrease pro-inflammatory cytokine production, and inhibit intracellular migration of early-stage inflammatory response (Lu, Wang, Chen, Jiang, & [name], 2020). A recent Nature publication from [name] and his team explore connections between antidepressant drug administration and cytokine signaling, providing compelling support for the use of antidepressants in inflammatory disease states. Several studies from [name] et al. indicate antidepressant use inhibits pro-inflammatory cytokine gene expression both *in vitro* and *in vivo*. Using [name] methods, we will assay and investigate cytokine expression in our control and experimental patients while utilizing the expertise that [name] and his University of Toledo researcher team has developed on this topic.

Further evidence for the efficacy of fluoxetine in decreasing the IL-6 response that stimulates the cytokine storm in COVID-19 infection comes from an analysis comparing the transcriptomes of cells lines treated with fluoxetine, dexamethasone (a steroid established to decrease IL-6), and 2 other antidepressants : bupropion and paroxetine to the transcriptome of the same cell line with a knock down in the IL-6 signal transduction molecule. This analysis was performed this week in the bioinformatics group in the Department of Neurosciences at University of Toledo and is illustrated

below. The concordance of the fluoxetine and IL-6ST knockdown cell lines is remarkably high, averaging over 0.7 . This concordance is greater than that seen with dexamethasone treatment, the standard anti-inflammatory steroid, and is higher than 2 other commonly used antidepressants, bupropion and paroxetine.

## **2. Objectives/Specific Aims**

**Aim 1:** Fluoxetine treatment begun early after COVID-19 infection will reduce hospitalizations, intubations, and death from COVID-19 and complications more than no medication

**Aim 2:** Fluoxetine will decrease intubations and mortality in patients hospitalized with COVID-19 infection greater than no medication.

**Aim 3 :** Fluoxetine treatment of COVID-19 infected patients will not cause significant side effects or increase morbidity and mortality compared to no medication

**Aim 4.** Collect blood samples from 40 subjects for future cytokine analysis: both subjects taking fluoxetine and not taking fluoxetine samples taken at baseline and weekly after study initiation.

[figure not shown]

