#### b) **Method of treatment assignment**

Single arm patient centered clinical trial

At study entry, participants will consent study participation via daily monitoring and will choose whether to participate in the activity monitoring, cytokine assessment and drug treatment portions of the trial. Participants who do not choose to take fluoxetine will serve as the control subjects. Additionally, patients will have the choice weekly to decide to start, continue, or discontinue the fluoxetine. See figure below :

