#### c) **Inclusion/exclusion criteria**

Inclusion : Patients aged 18 and above, able to give informed consent

COVID-19 test positive or presumptive positive awaiting COVID testin or results by following criteria: fever, cough and shortness of breath

Overall Study Exclusion Criteria :

Unable to give informed consent  
Prisoner/ institutionalized patient  
Under age 18

Exclusion from Fluoxetine Arm:

Active bleeding requiring blood products  
Bipolar disorder not on mood stabilizing medication\*  
Known allergy or hypersensitivity to fluoxetine  
Currently taking the following medications : MAO I, pimozide, thioridine  
Currently taking hydroxychloroquine  
Pregnant or breastfeeding (pregnancy questionnaire attached)  
For hospitalized patients : QTc greater than 500 ms  
\*Hospitalized patient may be on hydroxychloroquine if QTc<500 and the primary attending approves

Exclusion from Blood Sample Provision:

Pregnant  
Self-report of under 110 pounds

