**g) Variables**

Demographic information (age, gender, medical history, co-morbidities, etc.)
Medications
Symptom profile

 
• Number of days of symptoms prior to testing
 

 
• Epidemiologic information from CDC/Health Department surveillance interview
 

 
• Hospital Course
 

Days in Hospital, Intubation, Complications
Outcome: Never hospitalized, Hospitalized, Intubation, Death

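### Aim 1 is about fluoxetine begun early, but early is undefined, entry has no limit on day of illness, and the planned comparison takes no account of it

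*Combined protocol and SAP*

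**What the plan says.** - **Aim (2. Objectives/Specific Aims, Aim 1):** "Fluoxetine treatment begun early after COVID-19 infection will reduce hospitalizations". No number of days and no anchor date is given. Aim 2 separately covers patients already in hospital.
- **Entry (3 c, Inclusion/exclusion criteria):** "COVID-19 test positive or presumptive positive awaiting COVID testin or results by following criteria: fever, cough and shortness of breath". The overall exclusions are inability to consent, age under 18, and "Prisoner/ institutionalized patient". None concerns duration of illness or recovery. Patients in hospital may take fluoxetine subject to a QTc criterion ("For hospitalized patients : QTc greater than 500 ms").
- **Start of treatment (3 b, Method of treatment assignment):** those who decline fluoxetine are the controls, and "patients will have the choice weekly to decide to start, continue, or discontinue the fluoxetine".
- **Timing data (3 g, Variables):** "Number of days of symptoms prior to testing". The list also names a symptom profile and information from a health-department surveillance interview, whose content is not described. The tables in 3 h count from study entry and do not list an onset date.
- **Analysis (4, Planned data analysis):** rates in subjects who receive fluoxetine are compared with rates in those who do not, by t-test or chi-square test. No restriction, stratification or adjustment is mentioned.

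**The concern.** The aim makes a claim about timing, and nothing in eligibility, data collection or analysis delivers it. Someone with an old positive test who is three weeks into illness and recovering would count in Aim 1 in the same way as someone on day two.

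The first consequence is interpretation: a difference, or its absence, in such a mixture says nothing specific about early treatment. The second is bias. A late entrant has already passed through part of the risk of hospitalization without the event. Patients choose their own group, so the two groups may differ in day of illness at entry. That would shift the rates with no contribution from the drug, and a crude chi-square test would neither show nor remove the shift.

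**Working it through.** **1. The plan's own figure.** Inputs from 3 d: 10% versus 5% hospitalized, alpha 0.05, power 0.80, two thirds choosing fluoxetine (2:1). Sidedness is not stated; two-sided without continuity correction is used here.

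Pooled rate = (0.10 + 2 × 0.05)/3 = 0.0667.

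n (no medication) = [1.960 × √(0.0667 × 0.9333 × 1.5) + 0.842 × √(0.10 × 0.90 + 0.05 × 0.95/2)]² / 0.05² = (0.599 + 0.284)² / 0.0025 ≈ 311.6, rounded up to 312.

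This gives 312 + 624 = 936, as stated, with power 0.800. There is no arithmetic error; the issue is what the 936 subjects represent.

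**2. Aim against rules.**

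| Element | What Aim 1 needs | What the plan has |
|---|---|---|
| Definition | An anchor date and a limit | Neither |
| Entry | Some bound on day of illness, or a record of it | No bound |
| Treatment start | Interval from onset to first dose | Start possible in any later week; interval not listed |
| Timing variable | Onset to entry and to first dose | Symptom days up to the test; not available at entry for presumptive patients not yet tested |
| Analysis | Groups compared at similar days since onset | Crude comparison |

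Patients already in hospital at entry cannot have the Aim 1 hospitalization as a new event, yet section 4 does not set them apart.

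**3. Bias with no drug effect (illustration).** Assumed, not in the documents: early entrants have a 10% risk, late entrants 2%, and the late share is 10% in one group and 30% in the other.

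- 10% late: 0.9 × 10% + 0.1 × 2% = 9.2%
- 30% late: 0.7 × 10% + 0.3 × 2% = 7.6%

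The spurious difference is 1.6 percentage points, about a third of the planned 5-point contrast (1.6/5 = 0.32). The ratio is 7.6/9.2 = 0.83, or 9.2/7.6 = 1.21 if fluoxetine takers are the earlier group. Within strata the comparison is 10% versus 10% and 2% versus 2%, so stratifying on day of illness removes this shift.

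**4. Does excluding late entrants restore power?** Power = Φ[(|p1 − p2| − 1.96 × SE0)/SE1], where SE0 is the pooled and SE1 the unpooled standard error, starting from 312 and 624. The late share is again assumed, and equal in both groups.

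| Late share | All kept, late at zero risk | All kept, late at 2% with no drug effect | Late excluded, not replaced |
|---|---|---|---|
| 20% | 0.708 | 0.682 | 0.715 |
| 30% | 0.652 | 0.608 | 0.661 |
| 40% | 0.588 | 0.523 | 0.600 |

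In the zero-risk column both rates are multiplied by one minus the late share. In the last column the rates stay at 10% and 5% and the group sizes are multiplied by the same factor. Exclusion gains about 0.01 if late entrants are past risk, and 0.03 to 0.08 if they keep a 2% risk. It also removes 187 (20%) to 374 (40%) of the 936 subjects.

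**The case against.** **Early may simply mean before hospitalization.** Aim 1 sits beside an aim for hospitalized patients, and the trial is described as pragmatic. This reading is plausible and would justify broad entry. But the plan does not state it, does not limit the Aim 1 analysis to patients outside hospital at entry, and under this reading day of illness still confounds a comparison of self-chosen groups.

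**The rationale is not only about early use.** The background does say that "Pretreatment with SSRIs results in decreased destructive immune reactions across a variety of animal models", but it also proposes fluoxetine as an adjuvant in critically ill patients. This stands: the timing requirement comes from the wording of Aim 1, not from the background as a whole.

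**Timing may be partly recoverable.** For a patient with symptoms before a test, onset is the test date minus the recorded symptom days. Entry and prescription are scheduled events, and the intake form, chart review or surveillance interview may hold more. This also stands. A reader might infer that the listed variable is the only timing information and that repair is impossible; the documents do not support that, because the content of those forms is not shown. Gaps remain for patients tested before symptoms or not yet tested, and no derivation is planned.

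**Late entrants may be few.** The presumptive route requires current symptoms, so only the test-positive route could admit old infections. How many would enter is unknown.

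**Day of illness is one confounder among many under self-selection.** True, but it is the one that Aim 1 names, and it is cheap to record.

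**Conclusion.** The concern holds for the plan as written. The Aim 1 comparison can mix early with late entrants and be confounded by day of illness, so its result could not be attributed to early treatment. The 9.2% versus 7.6% example shows that a moderate imbalance could matter; it rests wholly on assumed risks and late shares and is not an estimate for this trial.

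Two stronger readings are not supported. One is that the trial cannot answer its question at all: that depends on dates that may be collected and on an analysis that can still be changed. The other is that lost power justifies excluding late entrants: without replacement, exclusion recovers little power when those entrants are past risk. The case for change is bias and interpretation. It is a change the sponsor should make.

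**What to change.** **Sections 3 g and 3 h:** record the symptom-onset date (or the positive-test date if there are no symptoms), the study entry date and the first-dose date, at the existing baseline call and physician interview.

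**Section 4:** for patients not hospitalized at entry, stratify or adjust the Aim 1 comparison by days since onset. Report the result also under a definition of early, with its anchor date, that the sponsor sets before data are reviewed. The documents give no basis for a particular number of days, and none is suggested here. If the sponsor prefers not to define it, remove the reference to early start from Aim 1 and from its conclusion.

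**Cost:** three dates on existing forms, some added analysis, and less precision in the early-entrant result than in the full set. Entry criteria and the rules for starting fluoxetine need not change.

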### 3. Methods

a) **Study Design** : Pragmatic Clinical Trial : Experimental and Observational

#### b) **Method of treatment assignment**

Single arm patient centered clinical trial

At study entry, participants will consent study participation via daily monitoring and will choose whether to participate in the activity monitoring, cytokine assessment and drug treatment portions of the trial. Participants who do not choose to take fluoxetine will serve as the control subjects. Additionally, patients will have the choice weekly to decide to start, continue, or discontinue the fluoxetine. See figure below :

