#### **Aim 1 : Hospitalization rates**

Assumptions:

1. 2/3 of patients who enter the trial will choose to take fluoxetine
2. 10% of COVID-19 + patients will progress to a clinical condition requiring hospitalization
3. Fluoxetine treatment decreases hospitalization rate by 50%

Sample Size : 312 in the no medication group and 624 in the 2 fluoxetine groups, for a total sample size of 936. This sample size is very achievable given the current coronavirus pandemic.

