**h) Procedures, interventions, schedule**

Week/Day	Patient Intervention	Setting/ Responsible Individual	Standard of Care	Research Purposes Only
1/1	Informed Consent	Phone/ research team	-----	Yes
1/1	Baseline Study Data	Phone/ research team		Yes
1	Blood Sample	Laboratory Services	Inpatient	outpatient
1	Physician Interview/ Medication Prescription	Phone/Study physician	----	Yes
Daily	Symptom/ Side effect Check In	Phone/ research team		Yes
Weekly	Physician Interview/ Medication Prescription	Phone/Study physician	----	Yes
Weekly or Change in Clinical Status*	Blood Sample	Laboratory Services	Inpatient	outpatient

\*Change in Clinical Status includes outpatient to inpatient, transfer to ICU, and intubation

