**Procedures:**

Instrument	Duration	Assessment Time Points	Frequency
Baseline Intake Form Chart Review Form 04/1/19-present Baseline Demographics and past medical history	30 min	Initial study entry	Once
PHQ-9	5 min	Initial Study Entry	Weekly
GAD-7	5 min	Initial Study Entry	Weekly
Columbia Screener-recent	3 min	Initial study Entry	-----
Symptom Checklist	5 min	(included in baseline)	Daily assessments
Columbia Screener – since last visit	3 min	-----	Daily assessments
Physician Interview/Medication Prescription	40 min	Baseline	weekly

Drug Distribution		Once, at entry	monthly
Blood Draw for future assessment of cytokine levels	60 min	Baseline	Weekly, as possible
Chart Review Followup		At study exit, one month, 3 months, 6 months and one year after study exit	See notes to left 5 data points From 4/1/19- 4/1/23

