#### **4) Planned data analysis**

Aim 1, 2, 3 : Descriptive statistics,

Compare rates of primary and secondary outcome measures in subjects receiving fluoxetine with those not receiving fluoxetine by Student t-test and Chi-square test as appropriate.

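### Section 4 does not say how participants who start or stop fluoxetine after entry are grouped; an ever-received grouping can bias Aim 1 in either direction

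*Combined protocol and SAP*

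**What the plan says.** Section 3b has participants decide at study entry; they "will choose whether to participate in the activity monitoring, cytokine assessment and drug treatment portions of the trial". It continues: "Participants who do not choose to take fluoxetine will serve as the control subjects". The section then makes the decision revisable: "Additionally, patients will have the choice weekly to decide to start, continue, or discontinue the fluoxetine".

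The Aim 1 sample size in section 3d rests on an uptake assumption, "2/3 of patients who enter the trial will choose to take fluoxetine", which gives 624 on fluoxetine and 312 on no medication. Aim 1 in section 2 reads "Fluoxetine treatment begun early after COVID-19 infection will reduce hospitalizations"; early is not defined. Section 3f gives the outcome as a hospitalization rate, without a time window.

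The comparative analysis in section 4 consists of comparing outcome rates "in subjects receiving fluoxetine with those not receiving fluoxetine by Student t-test and Chi-square test as appropriate". It gives no time zero and does not mention people who start late, stop, or start after admission. Fluoxetine in hospital is foreseen: Aim 2 concerns hospitalized patients, and section 3c has fluoxetine criteria specific to them.

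**The concern.** Two grouping rules are open. One fixes the group by the entry choice (section 3b). The other follows treatment actually received (the wording of section 4). They give different answers from the same data.

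Under an ever-received rule, someone who declines at entry and is admitted on day 3 stays a control. Someone who declines, is still at home on day 7 and then starts becomes a fluoxetine subject. The late starter had to remain out of hospital to qualify, and that admission-free time is credited to the drug (immortal time bias). If people who first receive fluoxetine after admission also count as treated, the opposite happens: they enter the fluoxetine group with the outcome already present.

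Hospitalization is the only efficacy outcome for which section 3d regards the sample size as achievable. The data safety monitoring board section also has three-monthly interim analyses that feed into early termination for benefit or harm. If the rule stays unwritten, it could be chosen after the data are seen.

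**Working it through.** **Plan's own figure.** Section 3d gives 10% vs 5%, alpha 0.05, power 0.80, allocation 1:2. Sidedness is not stated; two-sided reproduces the plan. With pooled rate (0.10 + 2×0.05)/3 = 0.0667, n = [1.96√(0.0667×0.9333×1.5) + 0.8416√(0.10×0.90 + 0.05×0.95/2)]² / 0.05² = 311.6. That rounds up to 312, with 624 on fluoxetine and 936 in total. Power is 0.80.

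**Model for a drug with no effect.** From the plan: N = 936, 624 choose fluoxetine at entry, 312 decline, 10% are hospitalized. Assumed, because the documents do not say:
- exponential time to admission, mean m = 6, 10 or 14 days;
- late starts on day 7 only, or on days 7, 14 and 21, with a constant probability q among decliners still untreated and not admitted;
- late starters make up 5, 10 or 25% of all users;
- no in-hospital starts, no confounding.

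By day d, a fraction H(d) = 0.10(1 − e^(−d/m)) has been admitted. Starters at the k-th opportunity number 312·q(1−q)^(k−1)·(1 − H(d)). Of these, 312·q(1−q)^(k−1)·0.10e^(−d/m) are admitted later.

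**Worked case: 10% late, m = 10, days 7, 14 and 21.** Late starters must number 624×0.10/0.90 = 69.3, which gives q = 0.087.
- Check: 312×0.087×(0.9497 + 0.913×0.9247 + 0.913²×0.9122) = 69.3.
- Admitted after starting: 312×0.087×(0.0497 + 0.913×0.0247 + 0.913²×0.0122) = 2.2.
- Ever-received: (62.4 + 2.2)/(624 + 69.3) = 9.3%.
- Never-received: (31.2 − 2.2)/(312 − 69.3) = 11.9%.
- Risk ratio 0.78 for a drug that does nothing.

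**In-hospital starts.** Move a fraction x of admitted never-starters into the fluoxetine group. The two rates are equal when both are 10%. With H_N admitted among n_N never-starters, x = (H_N − 0.10·n_N)/(0.90·H_N). In the worked case x = (29.0 − 24.3)/26.1 = 0.18, about 5 people.

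**Power under entry-choice grouping.** If fluoxetine halves admissions after it is started, the decliners' rate in the worked case becomes (31.2 − 0.5×2.2)/312 = 9.6%. Against 5%, the same formula gives power of about 75%.

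**All scenarios** (ranges over m and start pattern; significant means two-sided p < 0.05; the last column is entry-choice power under a true halving with no stopping):

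| Late share of users | Late starters (% of 312) | n_N | H_N | Null RR, ever-received | Significant | Break-even x | Power |
|---|---|---|---|---|---|---|---|
| 5% | 33 (11%) | 279 | 29.1–30.7 | 0.87–0.94 | 6–11% | 5–10% | 76–79% |
| 10% | 69 (22%) | 243 | 26.8–30.0 | 0.74–0.87 | 10–31% | 11–21% | 70–78% |
| 25% | 208 (67%) | 104 | 18.1–27.0 | 0.31–0.52 | 71% to nearly 100% | 47–68% | 43–70% |

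The 25% row is an upper-end case, since two-thirds of decliners would have to start later. At 10% late with x = 0.25, the risk ratio is 1.06–1.23, against the drug.

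**Entry-choice grouping, same null model.** 62.4/624 vs 31.2/312 is 10% in both groups: risk ratio 1.00 and about 5% significant results. That holds only because the model contains no self-selection.

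**The case against.** The strongest reply is that the plan already groups by the entry choice. Section 3b places the decision at study entry and makes non-choosers the controls. Section 3d sizes the trial on people who choose fluoxetine on entering, and treats the groups as two independent samples. The exclusion criteria and the timeline speak of a fluoxetine arm. The term ever-received appears nowhere. The figure that section 3b refers to was not in the copy reviewed and may show the grouping. All this stands, and a reader who infers that the plan has no grouping rule at all goes too far: it has a partial, entry-based definition of controls. What is missing is any statement that section 4 uses it, or of what happens to switchers. Section 4's own wording is about receipt, not choice.

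A reader might also infer that Aim 1 must favour fluoxetine. The documents do not support that. Aim 2 and section 3c provide for treatment in hospital, and at 10% late starters about 3 to 6 inpatients who start after admission are enough to cancel the bias. Counting them as treated fits poorly with Aim 1's early start, but section 4 does not rule it out.

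Finally, the size is assumed. With 5% late starters, false positives are little above nominal. That limits any claim about how large the bias will be, but it does not remove the gap in the rule.

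**Conclusion.** The concern holds as a gap in the analysis rule. Weekly switching, combined with a crude comparison by receipt and no time zero, outcome window or rule for switchers, leaves Aim 1 open to an analysis that is biased for an inert drug. The bias is towards benefit when late starts occur only before admission: risk ratio 0.74–0.87 with 10% late starters and no in-hospital starts. It shrinks or reverses when in-hospital starters count as treated, with break-even at about 11–21% of admitted never-starters. The omission is certain. The magnitude is not, because it depends on late-start rate, admission timing and in-hospital uptake, none of which the documents give. Entry-choice grouping removes this timing bias but not confounding by self-selection.

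**What to change.** In section 4, state the following.

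1. **Aim 1.** Include only participants not hospitalized at entry. Time zero is study entry (consent and baseline data, week/day 1/1 in section 3h). Groups are fixed by the fluoxetine choice at entry, whatever is started or stopped later. Count hospitalizations within one fixed, stated window. The step "Physician Interview/ Medication Prescription" is a poor time zero: the schedule dates its first occurrence only to week 1, and the documents do not say whether decliners have it.
2. **Choosers found excluded.** Say how people who choose fluoxetine but then meet a section 3c exclusion from that arm are grouped, by a rule that uses only information from entry.
3. **Aim 2.** Group by fluoxetine status at admission, or at entry for those enrolled in hospital, and report the two sets separately. Note that for those enrolled as outpatients this conditions on hospitalization, which Aim 1 says the drug changes.
4. **Adjustment.** Add an analysis adjusted for the baseline variables already listed in section 3g. A time-varying exposure analysis, with time before the first dose counted as unexposed, is optional support. State that confounding by self-selection remains.

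Items 1 to 3 cost wording, and item 4 modest analysis. The time-varying analysis also needs start and stop dates recorded at the weekly contacts: section 3g lists only medications, and "Drug Distribution" is scheduled at entry and monthly.

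The real cost is dilution by crossover. The 80% power should be qualified: about 70–78% with 10% late starters and no stopping, under the assumptions above. Restoring 80% in that case would take a total of about 1,000–1,220. Whatever total is kept should count only people not hospitalized at entry.
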